### **10.3 Other study parameters**

Quality adjusted life years will be calculated and described using means with 95%CI and direct and indirect costs will be calculated and described using medians and IQR, and also means with 95%CI based on bootstrapping separate per group. Differences will also be tested (using bootstrapping).

Modification of the treatment effect by (Age, gender, BMI, cartilage damage, and the presence of a neuropathic pain component) will be explored using state of the art methods in collaboration with the Julius Center. Subgroup effects for patients treated with a unicompartamental and total KP as initial treatment (or planned initial treatment when randomised to KJD) will be performed as well.

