### Tertiary Objective:

- To describe and compare productivity and healthcare costs between KJD and KP over 2 years.
- To compare knee flexion over time

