#### 8.1.2 Secondary study parameters/endpoints (if applicable)

- WOMAC sub-scores for pain, stiffness, and function (0-100)
- KOOS scores for Pain, Symptoms, Function in daily living (ADL), Function in sport and recreation (Sport/Rec), and knee related Quality of life (QOL) (all scored on a 0-100 scale)
- SF36 physical component score and mental component score (0-100)
- NRS-pain (0-10)
- Patient Acceptable Symptom State
- NRS-satisfaction (0-10)
- EQ5D-5L for generic Quality of Life
- Pain medication (custom made questionnaire to assess the use of pain medication during the assessment period (last week) of the KOOS pain questionnaire)
- (serious) adverse events; including pin-tract infections based on a custom made CRF.
- Occurrence of surgical reinterventions (KP and revision arthroplasty procedures)
- Radiographic Joint space width (for KJD only) in millimetres using KIDA (Knee Images Digital Analysis; 15) as well as overall K-L grade from the same image.

See Appendix A – N

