## **8.2 Randomisation, blinding and treatment allocation**

After written informed consent has been obtained and patients fulfil the eligibility criteria they are randomised via the EDC system (Castor).

Randomisation will be performed centrally using blocked-randomisation (random block size) stratified by center and gender using the validated randomization unit from Castor ([www.castoredc.com](http://www.castoredc.com)). This is an unblinded study.

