## 10. STATISTICAL ANALYSIS

### 10.1 Primary study parameter(s)

Given the obvious advantages of preserving a patients' own knee, KJD needs to demonstrate 'non-inferiority' on the medium-long (2 year) term.

A full statistical analysis plan (SAP) will be in place prior to the analysis of trial data. All analyses and patient populations will be predefined in this SAP. Both intention-to-treat (ITT) and per protocol (PP) analyses have biases so neither can be regarded the 'gold standard' for non-inferiority trials but these approaches can make critical differences to the results of a trial (18). The trial will be analyzed and reported according to CONSORT extension for Non-Inferiority and Equivalence Randomized Trials (19).

The primary endpoint, the total WOMAC score at 2 years, will be compared between groups using (multivariable) random effects (mixed) modelling to account for the nested and longitudinal structure of the data over the 24 months follow-up. In case residuals of the model are not normally distributed, transformed scores will be used in the regression modelling. In this analysis time will be used as a categorical variable (5, 8, 12 and 24 months), and an interaction between time and the treatment-arm variable will also be included. A random intercept at patient level as well as at center level will be included. The stratification factors for randomization, center (using a random intercept) and gender, as well as a limited number of a priori defined prognostic factors (i.e. baseline WOMAC total score, age, BMI, and severity of cartilage damage) will be accounted for in this analysis used as fixed covariates. Baseline WOMAC score will be used as a continuous covariate (similar to the outcome variable), as well as age and severity of cartilage damage which can be regarded a reasonable assumption given the limited, expected range (in patients with age  $\leq 65$  and severe knee OA (K&L grade  $> 2$ )). As we expect that the effect of BMI may be non-linear, we will use BMI as a categorical variable using the CDC classification (BMI  $< 18.5$ , underweight;  $18.5$  to  $<25$ , healthy weight; BMI  $25.0$  to  $<30$ , overweight; BMI  $30.0$  to  $< 35$  (max allowed in the study) obesity).

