## **10.2 Secondary study parameter(s)**

The analysis for continuous secondary outcomes follow the analysis strategy of the primary outcome. Binary, secondary outcomes will be compared using logistic multi-level regression analysis. The stratification factors for randomization (center and gender) will be used as (fixed) covariates in the analysis and the analysis will be adjusted by a limited number of a priori defined prognostic factors (e.g. baseline WOMAC total score, age, BMI, and severity of joint damage). Relative Risks (RR) with 95% confidence intervals will be estimated.

The upper limit (lower limit for response outcomes) of the confidence interval will be compared to the respective pre-defined non-inferiority limits to determine 'non-inferiority'. An ITT and a PP analysis will be performed.

The number of complications will be reported as the frequency and percentage of events and frequency and percentage of patients experiencing events per (type of) complication. Additional arthroplasty procedures, specifically a primary knee prosthesis after KJD and revision surgery (e.g. total after hemi prosthesis) after a primary knee prosthesis will be described per group.

Radiographic assessment of joint space width, as an indicator of cartilage repair, over a two-year period will be reported descriptively in the KJD group. Differences from baseline (pre-treatment) will be tested with paired t-tests or Wilcoxon rank sum tests depending on the distribution of the data at 1 and 2 years follow-up.

Missing data will be minimised using centralised data acquisition for all participating centers coordinated from the UMC Utrecht with appropriate monitoring on data queries and will be imputed using multiple imputation by chained equations for the analyses.

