### 11.2 Recruitment and consent

When a patient visits the outpatient clinic and is considered for a KP and can also be considered for KJD, the orthopaedic surgeon will inform the patient briefly about the study and both treatment options. If the patient is interested to participate, an appointment with the investigator and/or research nurse is made (can be directly after/during the clinic visit, or by telephone call). Both information regarding the study and information related to both treatment options KP and KJD will be provided. All information is also provided in writing (Patient Information Form for the study and information regarding both treatment options). As local treatment procedures (logistical and other, e.g. pre-operative work-up, number of days admitted, provision of physiotherapy, etc.) can differ between centres according to local practice this will be communicated as such to patients by the respective orthopaedic surgeon/centre according to local practice as this may be relevant for decision making in this pragmatic study.

Patients will be given as much time to consider their participation in the trial as needed, with a minimum of 1 week. Thereafter, the patient is asked by phone (or e-mail) by the investigator/research nurse for her/his decision. In case patients do refuse participation, regular care (KP) follows. In case patients are willing to participate they are invited for a screening/baseline visit. At this visit informed consent is signed by both patient and investigator/ research nurse.

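### Section 10.3 names no baseline or stratum adjustment for the bootstrapped comparison of QALYs and costs; as written it is valid but less precise than the collected data allow

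*Protocol*

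**What the plan says.** On QALYs, section 10.3 states: "Quality adjusted life years will be calculated and described using means with 95%CI". Costs are to be summarised by medians with interquartile range, and also by "means with 95%CI based on bootstrapping separate per group. Differences will also be tested (using bootstrapping"). No baseline value, centre or gender is mentioned for either outcome.

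The cost comparison is a tertiary objective in section 2: "To describe and compare productivity and healthcare costs between KJD and KP over 2 years". The Summary, however, lists productivity and healthcare cost among the main secondary outcomes.

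The modelled outcomes are treated differently. The primary model in section 10.1 includes "The stratification factors for randomization, center (using a random intercept) and gender, as well as a limited number of a priori defined prognostic factors", with baseline WOMAC among the latter. Section 10.2 carries this over: "The analysis for continuous secondary outcomes follow the analysis strategy of the primary outcome". Section 8.1.2 lists "EQ5D-5L for generic Quality of Life" as a secondary endpoint, so EQ-5D scores themselves fall under the adjusted strategy.

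Randomisation is "blocked-randomisation (random block size) stratified by center and gender" (section 8.2). The schedule in section 8.3 marks EQ-5D, MCQ and PCQ at baseline.

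**The concern.** QALYs are built from the EQ-5D responses that section 10.2 would analyse with adjustment, yet section 10.3 gives an estimator, an interval and a test for them without naming any. Two analyses of one instrument could then differ partly because one corrects for baseline and the other does not.

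For costs, section 11.2 gives a reason why centre may matter: "As local treatment procedures (logistical and other, e.g. pre-operative work-up, number of days admitted, provision of physiotherapy, etc.) can differ between centres". Admission days and physiotherapy are direct cost items, and centre is also a randomisation stratum.

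Two things are at stake. One is precision: variance that baseline values and strata could explain stays in the interval. The other is the realised estimate: if the arms happen to differ at baseline, an unadjusted difference carries part of that gap. Section 1 describes a reimbursement assessment that found the current evidence insufficient, so the economic results may well be used. If covariates were chosen only after the imbalance had been seen, the choice would be open to challenge.

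**Working it through.** **The plan's own figures.** The protocol gives no precision or power figure for QALYs or costs. Its only sample size is for the primary endpoint (section 4.4: margin 15, true difference 12, SD 15, 90% power, one-sided 2.5%). The normal approximation is 2 × 15² × (1.960 + 1.282)² / (15 − 12)² ≈ 525.4, so 526 per arm; the noncentral t version gives 527, as stated. Nothing below affects it.

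**Gain in precision.** With baseline-to-outcome correlation r, adjustment multiplies the standard error by √(1 − r²). The documents do not give r, so a range is shown.

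| Assumed r | √(1 − r²) | Interval narrower by |
|---|---|---|
| 0.1 | 0.995 | 0.5% |
| 0.3 | 0.954 | 4.6% |
| 0.4 | 0.917 | 8.3% |
| 0.5 | 0.866 | 13.4% |

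If the strata explained a further 5% of the variance (also an assumption), the factor would be √(1 − r² − 0.05): 0.927 at r = 0.3 and 0.837 at r = 0.5, or about 7% and 16% narrower.

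**Validity of the unadjusted comparison.** A simulation used 527 per arm, 28 strata (14 centres × 2 genders), no true difference and 1,500 replicates per setting. It took r from 0.1 to 0.6, with strata explaining 0% or 5% of the variance, and used the analytic standard error in place of the bootstrap one. The mean error of the unadjusted difference was at most about 0.003 SD. Its 95% interval covered in 93.7% to 96.3% of replicates. The width ratios agreed with the formula: 0.955 at r = 0.3 and 0.867 at r = 0.5 without stratum effects, 0.929 and 0.839 with them.

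**Chance imbalance in one realised trial.** Assume a baseline utility SD of 0.20.
- With 600 per arm, the standard error of the baseline difference is 0.20 × √(2/600) = 0.0115, and 95% of chance differences lie within ±0.023. With 527 per arm the limit is ±0.024.
- In units of the unadjusted standard error, the shift carried into the QALY difference is z × r, where z is the standardised imbalance. At the 95% edge (z = 1.96) and r = 0.3 to 0.5, this is 0.59 to 0.98. At the median absolute imbalance (z = 0.674) it is 0.20 to 0.34.

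**Route of the effect.** EQ-5D is repeated at 3 weeks. Under the trapezium rule, baseline carries half of a 3-week interval: (21/30.44)/12/2 = 0.029 year, which is 1.4% of 2 years. A baseline gap of 0.023 therefore adds only 0.023 × 0.029 ≈ 0.0007 QALY directly. The rest comes through correlation with later utilities. If all time points have equal SD and a common correlation ρ, the slope of QALY on baseline is 0.029 + ρ × 1.971. This is 0.42 at ρ = 0.2 and 1.01 at ρ = 0.5. Multiplied by the 0.024 limit, it gives shifts of about 0.010 and 0.024 QALY at the 95% edge.

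**The case against.** The strongest reply is that section 10.3 never says the comparison is unadjusted. The phrase about separate groups describes the per-arm intervals, and a bootstrap test of the difference is compatible with a bootstrapped regression. Section 10.1 defers all analyses to a SAP that is not shown, and covariates for an economic analysis commonly sit there. This stands as a limit on confidence: a reader might infer that the protocol rules adjustment out, and it does not. It does not dispose of the point, because section 10.3 states an estimator, an interval and a test without covariates, and followed literally these give an unadjusted contrast.

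A reader might also infer that chance imbalance makes the QALY difference biased or its interval invalid. The documents do not support that: under randomisation the estimator is unbiased and its interval already allows for chance imbalance, as the simulation shows. Nor does baseline utility matter much through its own share of the QALY area, which is about 1.4%.

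Nor is every other between-arm comparison adjusted. Section 10.2 reports complications as frequencies and percentages and describes additional arthroplasty per group. The contrast holds only for the modelled outcomes.

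Finally, the correlations and utility SD are assumed, and the larger shifts describe an imbalance at the edge of its 95% range. For costs the gain may be negligible. All of this stands.

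**Conclusion.** The point holds as a minor one. Section 10.3 names no adjustment for baseline EQ-5D utility, baseline MCQ/PCQ cost, centre or gender, although all of these are available and the modelled outcomes use comparable adjustment. The consequence is lost precision and an uncorrected chance imbalance in the realised estimate. It is not bias, invalid coverage or type I error inflation.

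The QALY interval would be about 5% to 13% narrower if the baseline-to-QALY correlation is 0.3 to 0.5. At a correlation of 0.1, which may be nearer the case for costs, it would be about 0.5% narrower. Any gain from the strata comes on top and depends on how much variance they explain. Confidence is moderate, because the text leaves room for adjustment and the SAP may supply it. The primary non-inferiority conclusion and the sample size are unaffected.

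**What to change.** In section 10.3, and in the SAP, state that:
- the QALY difference is estimated by regression on arm with baseline EQ-5D utility, centre and gender;
- the cost difference is estimated by regression on arm with baseline MCQ/PCQ cost, centre and gender;
- both regressions are run inside the planned bootstrap, resampling within arm;
- the per-arm means and medians remain as description.

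If the SAP already specifies this, a cross-reference in section 10.3 is enough. The cost is one or two sentences, with no new data, visits or patients. The covariates should be fixed before trial data are analysed, so that their choice cannot depend on the imbalance observed.

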Recently Zorg instituut Nederland (ZiN) performed an evaluation of the ‘state of knowledge and clinical practice (StWP)’ for KJD for the treatment of knee-OA indicated for a KP at a younger age (65 years). It was concluded that KJD is a promising treatment, but that the current evidence regarding this treatment is still insufficient for KJD to be eligible for reimbursement. Their judgement was mainly based on a small (n=20:40 patients) RCT comparing KJD to a total KP performed by our group (8). Patients showed no statistically

significant difference in patient reported efficacy outcomes between KJD and TKP, but the results seem to indicate that compared to KP, KJD is slightly less effective. See also table/figure below

This RCT was a comparison between KJD and a total KP. Roughly, there are two types of a knee prosthesis, a unicompartmental or total knee prosthesis. A total knee-prosthesis (TKP) has shown to be effective in reducing pain and regaining function. The average quality of life (utility) increases from 0.6 (preoperatively) to 0.85, indicating a substantial overall effectiveness (3). However, 20% of people are not satisfied and difficulties with kneeling and persisting pain commonly occur (4,6,7). Moreover, specifically when placed at a young age (<65 years), a significant number of patients will need revision surgery. Unicompartmental knee prostheses (UKP) are presently used in ~13% of all patients receiving a KP and specifically (in ~25%) in younger patients. Although, overall long-term results regarding revision rates are still less satisfactory, this may be due to the originally limited experience with the procedure. In centers implanting UKPs in higher numbers, UKP provides better long-term results that are comparable to TKP (11,12). Therefore, this type of KP is also suitable for younger patients.

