## **5. TREATMENT OF SUBJECTS**

### **5.1 Investigational product/treatment**

KP (total- or unicompartmental KP, at the discretion of the treating orthopaedic surgeon in consultation with the patient) is performed according to NOV guidelines as used in clinical practice.

KJD is performed according to the NOV recommendations for clinical care (see appendix S).

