### 8.1.4 Other study parameters (if applicable)

General demographics such as age, gender, BMI as well as clinical parameters such as previous surgery (Appendix P) at the index knee and current indication for type of KP (TKP or UKP) will be evaluated. Some of these are well known prognostic factors for the prognosis of knee OA and/or effectiveness of KP or KJD treatment (16) and as such may act as treatment effect modifiers which will be explored.

The (limited) preference patients (Appendix H) participating in the study may have for one of the treatments will be measured and the effect on treatment effectiveness explored. OA severity (measured by the Charnley score, Appendix I) and patients general health (ASA classification, Appendix J) will also be measured as a descriptive variable as well as to make future matching of patients to patients from the Dutch national registration of orthopaedic implants (LROI) possible (outside the scope of this proposal).

Finally, the Pain-Detect Questionnaire (Appendix K) will be assessed at baseline to identify neuropathic components of a patients' pain, which may also be relevant with regard to patients prognosis and treatment effects.

**For the GODIVA-bone substudy:** Evaluation of imaging markers will be performed in three stages.

In the first stage, bone parameters will be scored, as scoring would be easily feasible to apply in clinical practice for the assessment of suitability for KD treatment. From radiographs, subchondral bone structure, and osteophytes will be scored automatically, which can be done with KOALA software (ImageBiopsyLab; [Jansen M et al. Osteoarthr Imag 2022;100018]). From DEXA scans, the T- and Z-score output

will be used [Ishii Y et al. Open Orthop J 2016;10,]. From CTs, subchondral bone density, cysts and osteophytes will be scored using the OACT scoring system [Gielis W et al. J Pers Med 2020;11,]. From MRI scans, bone marrow lesions (BMLs) and cysts will be scored with the WOMBS scoring method [Roemer F et al. Osteoarthr Cartil 2016;24,].

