# only for patients treated with KJD

## only for patients participating in the GODIVA-bone substudy

1. At the study-specific baseline visit, after signing informed consent, in- and exclusion criteria will be formally checked. A radiograph of the knee is taken according to KIDA protocol (if a KIDA radiograph < 6 months is not available). This is in line with the KJD protocol for clinical practice recommended by the NOV (the Dutch orthopaedic society). If the patient is eligible, basic demographic and clinical information including the (limited) preference patients may have for any of the treatments is collected. In addition, questionnaires will be sent via email (via Castor EDC). When patients do not wish to receive digital questionnaires, they will receive paper versions by regular mail.
2. The patient will be randomized and will be informed about his/her allocated treatment (via phone or e-mail).
3. The patient will be invited for a pre-operative visit according to local clinical practice. During this visit, further details with respect to surgical and care practice (e.g. anesthesia) is provided in line with clinical practice in the respective centre. Surgery will be performed as soon as possible after this visit. Information about the techniques that are used for treatment (e.g. uni- or total prosthesis and type of distraction device), will be documented in Castor.
4. Surgery will be performed according to local clinical practice.

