#### **8.6 Follow-up of subjects withdrawn from treatment**

As KP and KJD are interventions during a (reasonably) short period we do not expect withdrawal from treatment. In the unlikely event a patient does not undergo the treatment he/she was randomized to, he/she will remain followed according to the protocol. Note that this can be only one way, refusing KP will not result in KJD as this is not approved reimbursed standard of care. Reasons for deviations from the treatment protocol will be recorded and the patients will be accounted for in the analysis appropriately (ITT and in PP these patients will be excluded).

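### The UKP/TKP subgroups are formed by implanted prosthesis in the KP arm but by planned prosthesis in the KJD arm, so randomisation does not protect these exploratory comparisons

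*Protocol*

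**What the plan says.** The subgroup rule is in Protocol section 10.3: "Subgroup effects for patients treated with a unicompartamental and total KP as initial treatment (or planned initial treatment when randomised to KJD"). The first half is about KP patients and uses the prosthesis they received. The bracket is about KJD patients and uses the prosthesis they would have received.

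Other sections bear on this rule:

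- Section 5.1 leaves the prosthesis type "at the discretion of the treating orthopaedic surgeon in consultation with the patient". Nothing fixes the type before randomisation or requires the implanted type to match the planned one.
- Section 8.2 stratifies randomisation by centre and gender, not by planned type, and states: "This is an unblinded study".
- Section 8.3 places randomisation and disclosure of the allocation in step 2. Step 3, the pre-operative visit, adds: "Information about the techniques that are used for treatment (e.g. uni- or total prosthesis and type of distraction device), will be documented in Castor".
- Section 8.6 provides for patients who do not get their allocated treatment: "In the unlikely event a patient does not undergo the treatment he/she was randomized to, he/she will remain followed according to the protocol". They stay in the ITT analysis and leave the PP analysis.
- Section 8.1.4 lists, among patient characteristics and without restriction to one arm, that "current indication for type of KP (TKP or UKP) will be evaluated".

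**The concern.** A subgroup comparison keeps the protection of randomisation only if the same rule, based on information that treatment cannot influence, places patients of both arms in the subgroup. Here the KP-arm classifier is realised at surgery, after allocation. A patient with a planned UKP who receives a TKP moves to the TKP subgroup if randomised to KP, while the same kind of patient randomised to KJD stays in the UKP subgroup. If such patients have a different prognosis, the results against UKP and against TKP mix the treatment effect with selection at surgery.

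There is a smaller, second gap in the ITT population. A KP-arm patient who receives no prosthesis was treated with neither type and falls in neither subgroup. A KJD patient with a recorded plan always has one.

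At stake is the reading of whether KJD compares differently with the two kinds of prosthesis. The primary analysis does not use prosthesis type and is not touched.

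**Working it through.** **Inputs from the protocol.** Section 4.4: SD 15, assumed true difference 12 points in favour of KP, margin 15, 527 patients per arm before allowance for loss. Section 1: UKP is "presently used in ~13% of all patients receiving a KP and specifically (in ~25%) in younger patients".

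**The protocol's own figure.** With 3 points between assumed difference and margin, n per arm = 2 × (1.960 + 1.282)² × 15² / 3² = 525.4, so 526; the version based on the t distribution gives 527 (power 0.9004). The 527 reproduces. The protocol gives no figure for the subgroup analysis.

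**Assumptions, not in the protocol.**

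- p, the share with a planned UKP, is 0.25. The protocol's figure describes UKP use in younger patients and is borrowed here as the planned share.
- s is the share of planned-UKP patients who receive a TKP when randomised to KP.
- d is how many points worse these patients score, in either arm.
- Switching goes in this one direction only. All other patients have the same mean within an arm, and the true treatment effect is the same in both subgroups.

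**Bias in the KP-minus-KJD difference (higher score is better).**

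- UKP subgroup: the KP arm has lost its switched patients and the KJD arm has not. Bias = s × d.
- TKP subgroup: the KP arm has gained them. Bias = −d × p × s / ((1 − p) + p × s).
- False interaction = UKP bias − TKP bias.

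**Central illustration, s = 10%, d = 10.**

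- Planned UKP per arm: 0.25 × 527 = 132; planned TKP: 395. Moved: 13.2 patients.
- UKP bias: 0.10 × 10 = +1.0.
- TKP bias: −13.2 × 10 / (395 + 13.2) = −0.32.
- Interaction: 1.0 + 0.32 = 1.32.
- SE for UKP after the move: 15 × √(1/118.8 + 1/132) = 1.90.
- SE for TKP after the move: 15 × √(1/408.2 + 1/395) = 1.06.
- SE of the interaction: √(1.90² + 1.06²) = 2.17.
- Unadjusted, a two-sided 95% CI would miss the true value 8.2% of the time for the UKP difference (1.0/1.90 = 0.53 SE) and 9.3% for the interaction (1.32/2.17 = 0.61 SE), instead of 5%.

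**Range.**

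| p | s | d | UKP bias | TKP bias | Interaction |
|---|---|---|---|---|---|
| 0.25 | 0 | any | 0 | 0 | 0 |
| 0.25 | 5% | 5 | +0.25 | −0.08 | 0.33 |
| 0.25 | 10% | 10 | +1.00 | −0.32 | 1.32 |
| 0.25 | 20% | 10 | +2.00 | −0.62 | 2.62 |
| 0.25 | 30% | 15 | +4.50 | −1.36 | 5.86 |
| 0.13 | 10% | 10 | +1.00 | −0.15 | 1.15 |

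**Check by simulation.** With 2,000,000 patients, a true difference of 12 in both subgroups, p = 0.25, s = 20% and d = 10, the rule as written gave 14.03 (UKP) and 11.35 (TKP), close to the 14.00 and 11.38 that the formulas predict. Classifying both arms by planned type gave 11.99 and 11.98.

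**The case against.** The strongest reply concerns weight. The analysis is exploratory, and a plan to predefine all analyses in a SAP is stated in section 10.1, so one sentence could be put right there. The magnitude is assumed throughout: the protocol gives neither a switch rate nor the prognosis of switched patients, a 10-point deficit is two-thirds of the SD, and even then the shifts are smaller than their standard errors. The sign would reverse if switched patients did better. Adjustment for baseline WOMAC, age, BMI and cartilage damage, if carried over from the primary model, would absorb part of the shift. All of this stands and limits the point to a recommended change.

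A second reply is that the planned type is probably recorded before randomisation already. Section 8.1.4 lists it with the demographics, and section 8.3 collects basic demographic and clinical information in step 1, before randomisation. That is the natural reading, but it is an inference: the schedule names only demographics and characteristics, not this item. It makes the fix cheaper; it does not change the rule in section 10.3, which still does not use this variable for the KP arm.

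A third reply is that the PP population comes first in section 10.1 and excludes a KP patient without a prosthesis. This is right, so the gap of patients who belong to neither subgroup exists only under ITT, and section 8.6 expects few of them. PP does not cure the main asymmetry, because it is defined by receipt of the randomised treatment (and a completed distraction period for KJD), not by agreement between planned and implanted type.

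**Conclusion.** The point holds. Section 10.3 states a different classification rule for each arm, and no other section applies the planned type to KP patients. This is a definition that the protocol fixes, not detail left open. The within-subgroup comparisons are biased whenever implanted and planned type differ for patients whose prognosis also differs.

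The size is unknown. It is zero without switching. Under assumed switch rates of 5–20% and deficits of 5–10 points it is 0.25–2.0 points for UKP and 0.33–2.62 points for the interaction, before covariate adjustment and with the direction resting on the assumption that switched patients do worse. Confidence is high about the asymmetry of the rule, not about any particular amount of bias. The primary non-inferiority conclusion is unaffected.

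**What to change.** Reword section 10.3 so that the subgroup in both arms is the TKP or UKP indication of section 8.1.4, recorded for every patient before randomisation. Estimate the subgroup effects through a treatment-by-planned-type interaction. Report the implanted type descriptively within the KP arm; if a comparison by implanted type is still wanted, label it a sensitivity analysis.

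Confirm that the baseline form captures the indication before allocation. If it does, the change is one sentence. If it does not, add one required field ahead of randomisation. This should be settled early: in an open trial, a plan written down after allocation can no longer be assumed independent of the arm, and a later SAP cannot recreate a record that was never made. No extra visits or patients are needed, and the choice of prosthesis at surgery stays as section 5.1 has it.
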